# 12.0 Drugs or Devices – N/A

# 13.0 Risks to Subjects

13.1 The focus group questions ask about attitudes, efficacy, and perceptions of sexual behaviors. This may be minimally uncomfortable psychologically for more conservative participants. Participants may decline participation at any time while in the study. Participants may also elect not to participate in discussing any question that they are not comfortable talking about. No procedures are in place by the PI personally to reduce the potential minimal psychological discomfort, other than encouraging and allowing participants

- to self-select out of the study if they are experiencing significant psychological discomfort.
- 13.2 Phase 2: The survey questions ask about sexual behaviors and prevention behavior. This may be minimally uncomfortable psychologically for more conservative participants. Participants may decline and stop participation at any time while in the study. Participants may also elect not to answer any question that they are not comfortable answering. No procedures are in place by the PI personally to reduce the potential minimal psychological discomfort, other than encouraging participants to self-select out of the study if they are experiencing significant psychological discomfort.

## 14.0 Potential Benefits to Subjects

There are no direct benefits for participation.

# 15.0 Provisions to Monitor Data to Ensure the Safety of Subjects – N/A

# 16.0 Withdrawal of Subjects

- 16.1 There are no anticipated circumstances under which subjects will be withdrawn from the research without their consent.
- 16.2 If a participant wishes to withdraw from the research during the focus group procedure (phase 1), they will be free to leave, the moderator will note this in her notes, and their audio data thus far will not be used during transcription and analysis. No further contact will be initiated by the researcher. If a participant wishes to withdraw from the research during the effectiveness phase (phase 2), they will be free to stop all study procedures at that time. As stated in the Cover Letter (consent information), they can call or email the study contact information and request that they be withdrawn from the study, so that no other follow up will be initiated. No further contact will be initiated by the researcher.

# 17.0 Costs/Payments to Subjects

- 17.1 There are no costs that subjects may be responsible for due to their participation in the described research.
- 17.2 Describe the amount and timing of any payments or inducements to subjects.

Phase 1: Participants will receive a Target, Wal-mart, or Amazon gift card in the amount of \$45 upon completion of the study procedures. Participants

will need to remain in the focus group throughout the duration prior to receiving any remuneration; the payment will not be pro-rated.

Phase 2: Upon pre-test completion, participants will be emailed (or pick up in person) a \$20 Walmart, Target, or Amazon gift card; \$80 Walmart, Target, or Amazon gift card upon post-test completion; and \$25 Walmart, Target, or Amazon gift card upon 3 month follow-up completion; for an opportunity to receive \$125 for complete participation. For participants who do not have email addresses, research assistants will assist them in obtaining one, if they wish, within the recruitment procedures; alternately, participants will be able to schedule a time to meet at one of the community centers in order to complete pre- and post-test surveys in person (on a university laptop), and/or to pick up gift card, if needed. At each survey activity (pre-test, post-test 3mo follow up), participants will need to electronically submit the survey prior to receiving any remuneration; the payments will not be pro-rated.

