# 4.0 Vulnerable Populations

- 4.1 Additional safeguards to protect their rights and welfare of economically and/or educationally disadvantaged persons.
  - Phase 1 (focus groups): Individuals who are economically/educationally disadvantaged: Participants' incentives for research participation are proportionate with the risks. Participants will be paid \$45 for their participation. Discomforts and inconveniences involved in the research, and financial or other gains are not overly compelling. Consent documents are written in language that is easily understandable to participant. Research team will read consent document out loud for each participant and participant will

have the ability to ask questions. Eligibility criteria includes the ability to read and speak English.

Phase 2 (effectiveness phase): Individuals who are economically/educationally disadvantaged: Participants' incentives for research participation are proportionate with the risks. Upon pretest completion, participants will be emailed (or pick up in person) a \$20 Walmart, Target, or Amazon gift card; \$80 Walmart, Target, or Amazon gift card upon post-test completion; and \$25 Walmart, Target. or Amazon gift card upon 3 month follow-up completion; for an opportunity to receive \$125 for complete participation. (For participants who do not have email addresses, research assistants will assist them in obtaining one; alternately, participants will be able to schedule a time to meet at one of the community centers in order to complete pre- and post-test surveys in person, (and/or to pick up gift card) if needed.) Discomforts and inconveniences involved in the research, and financial or other gains are not overly compelling. Consent documents are written in language that is easily understandable to participant. Participants will email or call a dedicated study email/phone line, where research assistants will screen them, answer any questions they may have, and get them formally consented and enrolled, if applicable. Eligibility criteria includes the ability to read and speak English.

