# **20.0** Provisions to Protect the Privacy Interests of Subjects

Phase 1: Participants will be told that they are not required to interact with anyone they do not wish during the group discussion. They will not have to give any written personal information except for signature on consent form. Participants will be told that they do not have to participate in discussion that they do not want to. Participants will also be told that if they feel uncomfortable or if any question is too intrusive, they can discontinue participation and help themselves to light refreshments upon leaving, without incidence or penalty.

Phase 2: Participants will be told that they are not required to answer any question that they do not feel comfortable answering. They will not have to give any written personal information except for email address, should they wish to have their gift card emailed.

Participants will be told that they can discontinue participation at any time, and/or withdraw themselves through emailing the study team (information found on Cover Letter – See Section 22.1).

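### Phase 1 participants are to be told they can leave without penalty, but leaving at any point forfeits the whole $45, which puts a cost on the plan's own safeguard for significant discomfort

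*Combined protocol and SAP*

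**What the plan says.** All references are to the combined protocol and SAP, Phase 1.

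- **Payment (17.2).** The payment is a single $45 gift card, given on completion. The condition is that those attending "will need to remain in the focus group throughout the duration prior to receiving any remuneration; the payment will not be pro-rated". Section 10.2 likewise places the card at the close of the session.
- **Risk (13.1).** The one risk named is discomfort from the topic: "This may be minimally uncomfortable psychologically for more conservative participants".
- **Response to the risk (13.1).** "No procedures are in place by the PI personally to reduce the potential minimal psychological discomfort, other than encouraging and allowing participants" to take themselves out of the study if the discomfort is significant. Just before that: "Participants may also elect not to participate in discussing any question that they are not comfortable talking about".
- **What participants are told (20.0).** If uncomfortable, "they can discontinue participation and help themselves to light refreshments upon leaving, without incidence or penalty". Also: "Participants will be told that they do not have to participate in discussion that they do not want to".
- **Withdrawal (16.2).** A person who withdraws is free to go, the moderator notes it, and that person's audio is not used. Payment is not mentioned.
- **Population and inducement (3.0, 4.1).** Eligibility requires residence in a low-SES neighborhood. Section 4.1, on safeguards for economically or educationally disadvantaged people, asserts that "financial or other gains are not overly compelling" and does not discuss the all-or-nothing condition.

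**The concern.** For discomfort that becomes significant, 13.1 relies on the participant leaving. That works best when leaving costs nothing, and 20.0 says it carries no penalty. Section 17.2 attaches the loss of the entire payment to the same act. The payment rule therefore pulls against the safeguard, in a group the protocol itself expects may include economically disadvantaged people.

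Little else is described for someone in that position. Safety monitoring is marked not applicable (15.0), and no psychological resource is expected to be needed (29.2). Consent is taken on the day of the session with no waiting period (21.1), so discomfort may first arise once the discussion is under way. At stake are the voluntariness of staying and the consistency of what up to 35 people are told about leaving.

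**Working it through.** The point rests on comparing passages and on simple arithmetic. The plan gives no statistical figure to reproduce.

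**Inputs**

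- Payment: $45, on completion only, not pro-rated (17.2).
- Script blocks: 35, 25, 20 and 10 minutes (10.3).
- Phase 1 size: 5 groups of 7 (5.3).

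**Step 1. Session length.** 35 + 25 + 20 + 10 = 90 minutes, which matches the 1.5 hours in 8.0 and 10.2.

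**Step 2. Payment by time of leaving.**

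| Leaves after | Minutes given | Paid under 17.2 | Forfeited |
|---|---|---|---|
| first block | 35 | $0 | $45 (100%) |
| second block | 35 + 25 = 60 | $0 | $45 (100%) |
| third block | 60 + 20 = 80 | $0 | $45 (100%) |
| stays to the end | 90 | $45 | $0 |

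The block on condom-use perceptions starts at 60 minutes. Someone who leaves then has given 60/90 = 67% of the session for nothing. This is only one possible exit point, since the first block already covers safer-sex messages. For scale, $45 over 1.5 hours is $30 per hour.

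**Step 3. Options for an uncomfortable participant.**

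| Option | Source | Payment |
|---|---|---|
| Stay and decline a question or discussion | 13.1, 20.0 | $45 (17.2 depends on remaining, not on speaking) |
| Leave | 13.1, 16.2, 20.0 | $0 |

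The first option is free of cost, but a silent participant still hears the discussion. The second is the one 13.1 names for significant discomfort, and the forfeiture attaches to it.

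**Step 4. Does any other passage pay an early leaver?** Sections 4.1, 10.2, 16.2, 17.2 and 20.0 were compared, and none does. Phase 2 differs: its $20 + $80 + $25 = $125 is paid by stage, so a person who stops later keeps what was already paid.

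**Step 5. Cost of paying leavers.** 5 x 7 = 35 participants, and 35 x $45 = $1,575, the sum that full attendance already commits. If k leavers are replaced, the extra is k x $45. The documents give neither k nor a replacement rule. As an illustration, k = 1 to 5 would add $45 to $225.

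**The case against.** The strongest reply is that participants have another way to cope: they may stay, say nothing on a topic and still be paid. That stands. A reader might infer that leaving is the only mitigation of any kind, and 13.1 and 20.0 do not support that. What remains is narrower: leaving is the only procedure named for significant discomfort.

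A second reply is that loss of a completion payment is not a penalty, and that the Phase 1 consent form, which is read aloud, may disclose the condition. The documents do not define the word, and the form is not among them. A reader might infer that participants are told something untrue, but that cannot be established here. The supported statement is that 17.2 and 20.0 are unreconciled. Disclosure in the consent form would not by itself reconcile them.

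A third reply is that the protocol rates the risk as minimal and the gains as not unduly persuasive. The rating of the risk bears on severity. The statement about gains is given without support. Equally, no passage shows that $45 would keep a distressed person in the room, so the reading that distressed people are paid to stay describes an incentive and not demonstrated behavior.

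Finally, a reader might infer that few departures would be taken as acceptance of the content. No passage uses departures that way. Phase 1 analysis is thematic analysis of transcripts (25.1), and a leaver's audio is not used (16.2).

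**Conclusion.** The concern holds in this form: 13.1, 17.2 and 20.0 conflict, and the payment rule puts a cost on the step the plan relies on for significant discomfort. The size is $45 of $45 for anyone who leaves before the end, among a planned 35 participants drawn from low-SES neighborhoods.

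The conclusion assumes that 17.2 is applied as written and that no unseen document pays early leavers. It does not assume that anyone will in fact stay against their wishes. The matter should be corrected before the focus groups run, but the potential harm is low. It is confined to Phase 1 consent and payment and has no bearing on the Phase 2 sample size or analysis.

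**What to change.** In 17.2 (Phase 1), replace the remain-to-the-end condition with a sentence such as: a consented participant who leaves early, for any reason, after the session has begun keeps the $45 card. Align 10.2, which now places the card at the close, check that 20.0 agrees, and state the same rule in the consent form.

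Deleting the no-penalty assurance from 20.0 and disclosing the forfeiture would make the text consistent, but is not recommended. It keeps the full forfeiture, removes an assurance to participants and leaves the cost on the safeguard.

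The change takes one sentence in 17.2 plus matching lines elsewhere. Spending stays within the planned $1,575 unless leavers are replaced, at a further $45 each; the protocol should say whether they will be. The downside is small: a few participants may leave early and still be paid.

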## 18.0 Compensation for Research-Related Injury – N/A

Research involves no more than minimal risk

## 19.0 Confidentiality

19.1 Phase 1: The PI will not be able to identify any individual's real identity during playback of the audio recordings, only their pseudonym. The PI will physically take digital audio data to the university and it will be downloaded with encryption immediately after each focus group on the PI's university office computer, stored there, transcribed, and analyzed on the PI's UH office computer. There will be nothing to connect the participant to any transcribed statement.

Phase 2: The PI will assign each enrolled and consented individual a unique ID number that will be matched to their email address via a study key code. Email addresses are needed in order to email each participant their e-gift card for participation, should they wish to receive it electronically. The study key code will be a spreadsheet and will be encrypted and located on the PI's secure university computer.

Phase 1: Study participation will collect consent forms that will not be linked to any audio file data and will be kept stored and locked in researcher's on-campus office. The consent form will include participant signatures which are direct identifiers. However, the consent form will not be linked to audio file data.

Phase 2: ID numbers will be linked to their pre, post, and follow-up assessment. Email addresses will be collected in the pre-test. This will be the only identifying information for study participation. An encrypted

spreadsheet will identify participant's email address and study ID number (study key code); stored on the PI's secure university computer. Email addresses are needed for the distribution of electronic gift cards. Gift cards will be emailed with encryption. If participants do not wish to provide an email address, they will be given the option to pick-up their gift card at a designated community center at each point of study participation (pre, post, and follow-up).

A certificate of confidentiality will be used in this research. The following language is documented in the consent form and cover letter:

"This research is covered by a Certificate of Confidentiality. The researchers with this Certificate may not disclose or use information, documents, or email addresses that may identify you in any federal, state, or local civil, criminal, administrative, legislative, or other action, suit, or proceeding, or be used as evidence, for example, if there is a court subpoena. Information, documents, responses, and/or email addresses protected by this Certificate cannot be shared with anyone else who is not connected with the research except, if there is a federal, state, or local law that requires disclosure. The Certificate cannot be used to refuse a request for information from personnel of the United States federal or state government agency sponsoring the project that is needed for auditing or program evaluation by the National Institute of Heath which is funding this project. You should understand that a Certificate of Confidentiality does not prevent you from voluntarily releasing information about yourself or your involvement in this research. If you want your research information released to an insurer, medical care provider, or any other person not connected with the research, you must provide consent to allow the researchers to release it."

- 19.2 No one outside the research team will have access to any identifiers.
- 19.3 The key to the study code will be destroyed following completion of all data collection procedures or at the end of study completion.
- 19.4 Phase 1: The recordings will be destroyed upon transcription.

# **20.0** Provisions to Protect the Privacy Interests of Subjects

Phase 1: Participants will be told that they are not required to interact with anyone they do not wish during the group discussion. They will not have to give any written personal information except for signature on consent form. Participants will be told that they do not have to participate in discussion that they do not want to. Participants will also be told that if they feel uncomfortable or if any question is too intrusive, they can discontinue participation and help themselves to light refreshments upon leaving, without incidence or penalty.

Phase 2: Participants will be told that they are not required to answer any question that they do not feel comfortable answering. They will not have to give any written personal information except for email address, should they wish to have their gift card emailed.

Participants will be told that they can discontinue participation at any time, and/or withdraw themselves through emailing the study team (information found on Cover Letter – See Section 22.1).

### 21.0 Informed Consent Process

- 21.1 The researcher will be obtaining consent:
  - Phase 1: Consent will take place in a closed-door conference room at Jacob's Group Home conference room on the day of anticipated study participation. Phase 2: Consent will take place via the "accept" button on the electronic survey (See Section 22.1).
  - There is no waiting period between informing the prospective subject and obtaining the consent.
  - Phase 1: There will be no ongoing consent. Participation is cross-sectional, meaning no other participation is required upon completion of their focus group. Additionally, participants who were a part of a previous focus group will not be allowed to attend or participate in a subsequent focus group.

Phase 2: There will be no ongoing consent. Consent to the initial pretest (in the form of electronic cover letter – See Section 22.1) will consent participants for the current data collection and follow-ups. Participants are able to leave any question blank they do not wish to answer, or withdraw from the study any time, via email, and no further contact will be initiated (-as stated in the Cover Letter consent information document).

• I will be following "SOP: Informed Consent Process for Research (HRP-090)."

Non-English Speaking Subjects: N/A

Waiver or Alteration of Consent Process (consent will not be obtained, required information will not be disclosed, or the research involves deception):  $N\!/\!A$ 

Subjects who are not yet adults (infants, children, teenagers): N/A

**Cognitively Impaired Adults:** N/A **Adults Unable to Consent:** N/A

# 22.0 Process to Document Consent in Writing

22.1 Phase 1: I will be following "SOP: Written Documentation of Consent (HRP-091)."

Phase 2: We are requesting a Waiver of Written Consent because survey data collection will be obtained online through a secure survey portal. This research presents no more than minimal risk of harm to subjects; and the

research procedures include activities that would not require written consent outside of the research context. Consent information will appear as a cover letter on the first page of the online survey, followed by confirmation (click "accept" button) that the participant has read the consent information and agrees to take part in the research. If a participant disagrees, the survey is closed. If a participant agrees, their response is recorded as a part of their survey data.

- 22.2 Written Consent form for phase 1 is attached in SmartForm
- 22.3 Cover letter (consent information) for phase 2 is attached in SmartForm
- **23.0** HIPAA- N/A
- 24.0 FERPA N/A

## 25.0 Data Management

- 25.1 Phase 1: Data Analysis will include transcribing the focus group data, examining all the transcriptions aggregately and analyzing the qualitative data for common themes, as thematic analysis will constitute the analysis procedure.
  - Phase 2: Data analysis will include aggregating the data, eliminating any identifiers, and performing repeated measures t-tests on the study variables of interest.
- 25.2 Phase 1: Electronic data (audio files and transcripts) will be secured and encrypted on my on-campus university computer in my office. Consent forms, will be stored in separate folders in a locked file cabinet.
  - Phase 2: Electronic data will be secured and encrypted on my on-campus university computer in my office. Study key code spreadsheet (linking participant ID number with email address) will be encrypted and stored securely on my office computer.
- 25.3 Data will be stored for seven years
- 25.4 Only the PI (researcher) and approved student research team members will have access to the raw data.
- 25.5 The PI (researcher) will be responsible for receipt of the data (Both Phases).
- 25.6 Phase 1: One approved student research team member will have access to the audio files and will be responsible for all audio transcription.Transcription will take place only on the PI's university-issued laptop within the researchers' office during student researcher's work hours. Audio transcription files will be password protected on the UH secure server.

Phase 2: Approved student researchers will have access to the de-identified data. All data analyses will take place only on the PI's university-issued laptop within the researchers' office during student researcher work hours.

25.7 Data will not be banked for future use.

